2.1 Risk / Benefit Assessment

This study involves minimal risks not materially greater than those that may be experienced in usual care. Men receiving the DSI may not have yet been exposed to the level of detail contained in the decision aid. Some men might react negatively to the detail. However, generally decision support is not associated with harms such as anxiety or distress, and the coaching session is designed to help men absorb the information in the decision aid and write up questions in a question list. We cannot be sure that men will benefit directly, however the study will add important knowledge to our scientific understanding of how best to educate men about treatment options for early-stage prostate cancer. These insights could shape decision support for years to come. Therefore, the potential benefits outweigh the risks.

3 STUDY OBJECTIVES

3.1 Primary Objective

The primary objective is to increase the rate of *informed* decision-making among men with early-stage prostate cancer.

3.2 Secondary Objectives

Secondary objectives relate to assessing the effect of decision support on anxiety, decision self-efficacy, and decision quality, as measured by validated survey instruments, and management choice.

3.3 Optional Biospecimen Banking

In the future, we may also request archival leftover tumor tissue from a participant's recent prostate biopsy and saliva for banking for future research. If the scientific team were to decide to proceed with banking biospecimens we would do so based on tissue studies associated with the CaPSURE™ study (IRB # 10-00881) and its related sub-study CaPSURE Tissue (IRB# 13-12624).

4 STUDY DESIGN

4.1 Study Overview

This is a four-site, site-randomized, two-period, cluster-crossover design. 160 subjects are planned. Sites will be randomized in pairs to period 1 usual care or intervention. After all sites have met accrual goals, the pairs will cross over to intervention or usual care. In usual care, study participants will complete surveys and prepare for their visit as they usually would, and receive whatever education materials and counseling is normally provided by the sites. We will assess the materials and counseling received by surveying the patients about this. In the intervention, subjects will be contacted by the coordinating site (UCSF) and offered educational materials that include personalized risk estimates, along with coaching to help list questions for their upcoming visit with the urologist.

5 CRITERIA FOR EVALUATION

5.1 Primary Efficacy Endpoint

The primary endpoint is the proportion of patients who respond accurately to two survey items assessing whether they are more likely to die of prostate cancer or other causes (other causes are more likely); and whether waiting three months to make a treatment decision will affect their survival a lot; somewhat; or a little or not at all (a little or not at all is the correct answer).

Knowledge of these key facts is an important endpoint because patients often associate the word cancer with high mortality risks, and with urgency to act. Patients also often associate more invasive treatment with greater benefit.

In the case of early-stage, low-risk prostate cancer, patients should recognize that early-stage prostate cancer patients are more likely to die of other causes than prostate cancer; and that most can safely take three months to make decisions. This knowledge opens patients up to consideration of active surveillance along with surgery and radiation therapies.

Our intervention aims to educate patients about their (low) mortality risk and the time available for decision-making after their cancer diagnosis **before** they see their urologist for primary treatment counseling. Therefore, we will assess this endpoint just prior to the first urology appointment after a biopsy confirms early-stage low-risk cancer, and compare the usual care results to the intervention arm.

In preliminary studies at an academic medical center with highly educated patients, our intervention increased the proportion of patients responding accurately from 69% to 88%. Meanwhile, at our community sites, 52% of usual care patients responded accurately. We hypothesize that in our randomized controlled trial, we will see over 75% of patients respond accurately in the intervention arm, versus 50% in the usual care arm.

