PLANNED INTERIM ANALYSES	As a behavioral intervention trial testing knowledge as the primary outcome, there an interim analysis is not planned.

STATISTICS Primary Analysis Plan	We will use univariate statistical tests (e.g., chi-square, t-test) and multivariate regression to assess the difference in the probability of the primary outcome between subjects randomized to the intervention and control arms for each site.
Rationale for Number of Subjects	Standard power calculations for chi-square tests to compare two proportions along with adjustments for potential correlation of responses within sites, missing data and attrition show that tests based on a sample of 136 subjects would have power to detect an alternative where the probability of the primary response increases from 0.5 in the control sites to 0.75 in the intervention sites. We will enroll 160 subjects to allow for attrition and survey non-response.

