15.3 Analysis of Primary Endpoint

The primary statistical analysis will compare the probability of correctly responding to the two knowledge survey questions between subjects randomized to the intervention and control sites using logistic regression. The primary predictor of the logistic model will be the binary, site-specific intervention indicator. We will also include site, time and intervention group by time interaction terms. Since randomization by site may not balance, all relevant sociodemographic and clinical characteristics of the subjects may be included in the models; we will also include other factors that are not balanced between the groups. We will assess balance by comparing means of continuous characteristics using two sample t-tests and by comparing categorical characteristics using chi-square tests.

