15.6 Sample Size and Randomization

We will base sample size calculations on the comparison of the probability of correctly responding to the two survey questions between subjects at the intervention versus control sites with a design effect correction to accommodate the potential correlation of responses within sites [44]. That is, we will inflate the sample sizes resulting from standard sample calculations for the comparison of two proportions by the design effect, $1 + (n-1)*\rho$, where n is the sample size per site and ρ is the intraclass correlation coefficient of the primary binary response[45]. We are interested in detecting an alternative where the probability of the primary response increases from 0.5 in the control sites to 0.75 in the intervention sites. Standard power calculations for chi-square tests to compare two proportions [45] show that tests based on a total sample size of 116 would have power 0.8 to detect the alternative of interest. Since our study design involves 8 clusters (four sites measured in two time periods), our initial design would include 15 subjects measured in each site at each time. Preliminary data indicate that the intraclass correlation coefficient of the primary response is quite low within sites; the estimated intraclass correlation coefficient was less than 0.01. This estimate produces a design effect of 1.14 and we inflate the required number of subjects per site and time to 17 for a total sample size of 136.

Randomization: At baseline, this study will randomize two sites to the intervention and two sites to serve as controls. There are six possible assignments of two intervention and control sites in our study and we will generate a uniform (0,1) random number to select one of them.

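### Section 15.3 names no effect measure or interval, and its logistic arm coefficient cannot be set against the 25-point hypothesis without a conversion the plan does not specify

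*Combined protocol and SAP*

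**What the plan says.** Four places put the primary question on the probability scale.

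- Section 5.1, endpoint: "The primary endpoint is the proportion of patients who respond accurately to two survey items".
- Section 5.1, hypothesis: "we will see over 75% of patients respond accurately in the intervention arm, versus 50% in the usual care arm".
- Section 15.6, sizing: the alternative is that "the probability of the primary response increases from 0.5 in the control sites to 0.75 in the intervention sites", with the total taken from a chi-square comparison of two proportions.
- Protocol Synopsis, Statistics: univariate tests such as chi-square, together with "multivariate regression to assess the difference in the probability of the primary outcome".

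Section 15.3 also words its aim as comparing the probability of a correct response, "between subjects randomized to the intervention and control sites using logistic regression". The arm indicator is the primary predictor. Site, time and an intervention-group-by-time interaction are added, and sociodemographic and clinical covariates may be.

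No section names the quantity to be reported (difference, ratio or odds ratio), a confidence interval, or a way to get from the fitted model to arm proportions. Section 15 says that a SAP describing all analyses will be written before the final data are analysed.

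**The concern.** A logistic model estimates the arm effect as a log odds ratio, conditional on the other terms. If the coefficient is reported as it stands, the primary result appears on a different scale from the hypothesis. An odds ratio near 3 is easily read as a threefold improvement, when 50% to 75% is a ratio of 1.5.

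The group-by-time term makes this worse. With an interaction in the model, the arm coefficient refers to one reference period, not to the trial as a whole. In this design the term also cannot be separated from fixed site effects, so the value of the coefficient depends on how the software resolves the redundancy.

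At stake is how the primary result is stated and read. The power of the trial is not in question.

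**Working it through.** **1. The plan's own figure.** Inputs from section 15.6: 0.50 versus 0.75, power 0.80. Alpha is not stated; I assume two-sided 0.05. The pooled two-proportion formula without continuity correction gives 58 per arm, 116 in total, which matches "tests based on a total sample size of 116 would have power 0.8 to detect the alternative of interest". Design effect: 1 + (15 − 1) × 0.01 = 1.14. Then 15 × 1.14 = 17.1, taken as 17, and 17 × 8 = 136. Both totals reproduce.

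**2. The two scales on the plan's figures (section 5.1).** Odds ratio = [p1/(1 − p1)] / [p0/(1 − p0)].

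| Comparison | Difference | Odds ratio |
|---|---|---|
| Hypothesis, 50% to 75% | 25 points | (0.75/0.25)/(0.50/0.50) = 3.00 |
| Pilot, 69% to 88% | 19 points | (0.88/0.12)/(0.69/0.31) = 7.333/2.226 = 3.29 |

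The smaller gain has the larger odds ratio. This needs no assumption.

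**3. What an odds ratio of 3.0 means without covariates.** p1 = 3·odds0/(1 + 3·odds0). At the 52% seen in usual care at the community sites, p1 = 0.765, a gain of 24.5 points. At the academic pilot's 69%, p1 = 0.870, a gain of 18.0 points.

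**4. Covariate adjustment.** I integrated over a normal covariate score on the logit scale and solved for marginal rates of 0.50 and 0.75. The score's SD is the free input.

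| Logit SD | Conditional odds ratio for 50% to 75% | Gain if the conditional odds ratio is 3.0 |
|---|---|---|
| 0.2 | 3.03 | 24.8 points |
| 0.5 | 3.19 | 23.9 points |
| 1.0 | 3.72 | 21.4 points |
| 1.5 | 4.62 | 18.6 points |

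Only the first row has support in the documents, and only for site. An intraclass correlation of 0.01 at a 50% rate is a between-site variance of 0.01 × 0.25 = 0.0025, an SD of 0.05 in probability, and 0.05/0.25 = 0.2 on the logit scale. The other rows are assumptions.

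**5. The group-by-time term.** Let A = 1 for DSI, T = 1 for period 2, and S = 1 for the two sites that start in usual care. Sites starting with DSI have (A, T) = (1, 0) then (0, 1). The others have (0, 0) then (1, 1). In all eight site-periods

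A × T = (A + T − 1 + S)/2,

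and S is the sum of two site indicators. Intercept, arm, time, three site indicators and the interaction are seven columns of rank six. Reading group as starting sequence changes nothing, because S × T is the same column as A × T. The result holds when time is the two-level period and site is a fixed effect.

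The model fits equally well whichever redundant column is dropped, but the arm coefficient changes. As an illustration, take a true arm odds ratio of 3.0, no period effect, and the two S sites higher by 0.2 logits (assumed, borrowing the SD from step 4). Dropping the interaction gives an arm odds ratio of 3.0. Dropping an S-site indicator gives 3.0 × e^(−0.2) = 2.46, and making period 2 the reference gives 3.0 × e^(0.2) = 3.66. Averaged predictions give 52.5% in usual care and 76.8% in DSI, a difference of 24.3 points, under all three codings.

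**The case against.** The strongest reply is that the plan never says it will report an odds ratio. Both 15.3 and the synopsis word the target as a probability, a fitted logistic model yields probabilities directly, and the synopsis's chi-square comparison sets the two arm proportions side by side. A reader might infer that the plan has chosen the wrong scale, or that its result can never be compared with 75% versus 50%. The documents support neither. What they show is a missing specification, and the conversion can be made from the same model.

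The crude comparison is also better than it might look. If accrual holds, each site contributes 20 men to each arm, and two sites use each arm in each period, so site and period are balanced. The crude difference would then be little confounded by them. It still leaves out the terms of the primary model, and no interval is specified for it.

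A reader might also expect the adjusted odds ratio to reach 3.7 or 4.6. That requires covariates with a logit SD of 1.0 or 1.5, and nothing in the documents shows that age, race or PSA predict these two survey items so strongly. Likewise, the 18-point reading at a 69% control rate belongs to the academic pilot, whereas this trial uses community sites.

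Finally, the promised SAP is a natural home for an effect measure. That is fair, but section 15 does not say that the SAP will define one, and the group-by-time problem sits in the model that 15.3 already states.

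**Conclusion.** The concern holds as an omission. Endpoint, hypothesis, sizing and synopsis target are proportions or a difference in probability, yet 15.3 stops at a logistic model. Its arm coefficient is conditional and, with the group-by-time term, not an overall effect. It cannot be compared with the 25-point hypothesis until a conversion is specified.

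The firm evidence on size is the reversed ranking in step 2, which uses the plan's figures alone, and the exact redundancy in step 5, which assumes fixed site effects and a two-level period. Near the expected community control rate the practical distortion is small: an unadjusted odds ratio of 3.0 is 24.5 points at 52%. The figures for covariate SDs of 0.5 and above are illustrations and carry no weight in the rating.

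A reader might infer that the trial is wrongly sized. It is not: 116 and 136 both reproduce, and neither depends on the scale of reporting. Severity: minor.

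**What to change.** In section 15.3, and in the SAP when it is written:

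1. Keep logistic regression with arm, site and period for the hypothesis test.
2. Take the group-by-time term out of the primary model. With fixed site effects this loses no fit, because the term adds no information beyond arm, time and site.
3. Define the primary estimate as the standardised difference in proportions: average the model's predicted probabilities over all analysed men with arm set to DSI, then with arm set to usual care, and subtract.
4. Report both proportions and their difference with a 95% confidence interval, using the same variance method as the test.
5. Report the odds ratio as supplementary.

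The cost is a few lines of text and code. No new data are needed and the sample size does not change. The result then directly answers the synopsis's question about a difference in probability.

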5.2 Secondary Efficacy Endpoints

We will assess the impact of our intervention on decision self-efficacy, decision quality, anxiety, and satisfaction, based on participant responses to validated surveys. We will also measure patient understanding of reclassification risk, based on a custom survey designed for this study. (Please see Table 2 for further details on study schedule)

We will measure decision self-efficacy before and after the intervention (before the medical appointment); to assure that the intervention is working as intended. In prior studies we and other researchers have shown that similar pre-consultation decision support interventions are associated with pre/post increases in decision self-efficacy. In the usual care arm, we will measure decision self-efficacy before the medical appointment.

We will measure decision quality, anxiety, and understanding of reclassification risk before and after the medical appointment. The study will record management or treatment approach selected by the participant.

We will measure satisfaction after the medical appointment.

5.3 Safety Evaluations

There are no anticipated clinical or physical risks associated with participation in this study. The primary anticipated risks associated with this study are losses to privacy, or anxiety or discomfort associated with the survey questions. Participants will be told that their participation is voluntary, and participants will be allowed to skip questions. The key questions that we want participants to answer (or be considered as having missing answers on primary outcomes) are 2 knowledge questions. In our sample size calculations, we will conservatively plan for around 10% missing responses (N~15) on our primary outcome, as well as 10% attrition (N~15 subjects) from consent to visit.

5.4 Other Evaluations

We will measure covariates that will inform exploratory analyses, including quality of life (SF-12 [30, 31], EPIC [32], diet and lifestyle (D&L) [33], decision self-efficacy (DSE), control preferences scale (CPS) [34], choice disposition (CP) [35], and demographics.

6 SUBJECT SELECTION

6.1 Study Population

Subjects with a diagnosis of low-risk prostate cancer (PCa) who meet the inclusion and exclusion criteria will be eligible for participation in this study.

6.2 Inclusion Criteria

1. Male \geq 18 years of age and newly diagnosed PCa (within 3-months).
2. Documentation of a low-risk PCa diagnosis as evidenced by clinical features of the following criteria:
 - a. PSA test at diagnosis \leq 15 ng/ml
 - b. Localized PCa (cT1/T2,N0,M0)
 - c. Biopsy Gleason grade 2-6 OR (or 3+4 AND \leq 33% cores are positive for adenocarcinoma)
 - i. A minimum of 10 diagnostic cores taken by a systematic directed approach. Sampling may be obtained by target TRUS or MRI imaging.
 - d. No treatment yet
 - i. No previous radiation or simultaneous use of androgen deprivation
 - ii. Prior use of 5-alpha reductase inhibitor is allowed if they have been stopped for 6 or more months and biopsy performed when patient was not taking the drug
 - e. English language proficient and ability to provide ICF
 - f. Managing urologist considers them a candidate for active surveillance
3. Written informed consent (and assent when applicable) obtained from subject and ability for subject to comply with the requirements of the study, including the ability to read and speak English.

6.3 Exclusion Criteria

Participants will be ineligible if they: 1) have pursued any active therapy for prostate cancer will be excluded; 2) are unable to read/speak English; or 3) if their managing urologist does NOT deem them as a candidate for active surveillance.

7 CONCURRENT MEDICATIONS

All subjects should be maintained on the same medications throughout the entire study period, as medically feasible, with no introduction of new chronic therapies.

7.1 Allowed Medications and Treatments

Standard therapy for non-prostate cancer conditions is allowed throughout the study. After the active intervention is completed and primary and secondary outcomes have been assessed (shortly after the visit with the managing urologist), the participant may pursue whatever

treatment he chooses for his prostate cancer. At this point, the participant will roll-over to an observation phase only.

8 STUDY TREATMENTS

8.1 Method of Assigning Subjects to Treatment Groups

The trial will use a randomized crossover design using 4 community-based urology sites. Two sites will be randomized to initiate the study in the ‘decision support coaching intervention’ arm while the remaining 2 sites will start in the ‘usual care arm’. Each site will accrue 20 participants before crossing over to the alternate arm (see Figure 1). A total of 160 newly diagnosed men who are pre-treatment with low risk prostate cancer will be enrolled into the study. If the participating site is unable to meet the recruitment goal of 40 participants per site (for a final sample of 160 participants); the investigators may add sites to achieve the final study sample size of 160 during the funding period of this grant.

8.2 Blinding

The participating site will be randomized to DSI or usual care at study initiation and will crossover once they have met their accrual goal of 20 participants (see Figure 1). Patients recruited at each site will be blinded to the assignment of their site. Patients will be informed during recruitment and consent that the study will give surveys to assess patient knowledge and related outcomes at four sites, and examine how variations in patient education strategies are associated with patient survey responses. The clinic staff and physicians will NOT be blinded to the assignment; however, the primary outcome will be determined before the patient conducts their decision making consultation with the physician. The statistician will remain blinded to the randomization status of the sites during the analysis phase only.

8.3 Decision Support Intervention

Participants randomly assigned to the Intervention will receive access to our decision aid, developed following the International Patient Decision Aids Standards with the input of patients, family members, physicians, nurses, clinic staff, decision scientists, and clinical researchers [1]. After reviewing the decision aid, either via a secure website or a PDF file emailed to them (whichever is most convenient for them), patients will speak with a trained coach. The coach will review the decision aid screen by screen, or page by page, and write down any questions that the patient voices about the contents of the decision aid. The coach will then review the decision aid help text to address questions that are covered there, and save the remaining questions for the attention of the attending urologist at the upcoming visit. Specifically, the coach will save a word-processed document with the patient’s questions for the physician, and send that file to the site study coordinator, who will print copies for the patient, family, and physician and make those copies available to all parties at the time of the clinic visit. Our surveys will also assess what other decision or communication aids the patient may have accessed on their own prior to the visit.

Our decision aid incorporates the following estimates:

- Survival and quality of life outcomes from the CaPSURE outcomes database for patients who underwent active surveillance, surgery, or radiation.

- Risk of reclassification (“upstaging” or “upgrading”) based on demographic, clinical, and pathologic parameters using a model developed at UCSF and tested using UCSF and CaPSURE data.

